After the research coordinator completes the verbal consent process and the 1-month Decisional conflict assessment, s/he will then invite the patient to participate in the one-hour ASK Coaching session. (See attached Aim 3 additions to invitation phone call Coaching invitation). The coordinator will review the Coaching session Fact Sheet and answer questions. Participation in the Coaching session is not mandatory, but is encouraged as a way to review the information in the ASK report, and coach patients to use the information when discussing treatment options with their medical team. The session is 1 hour and uses a virtual Zoom web-platform. Participants can also opt to join by phone alone. Sessions will be scheduled weekly, alternating between mid-day and early evening to meet participant needs, and led by a trained health educator. The session will not offer clinical advice. (See Coaching session script and ASK Coaching Power-point slides.)

Participants scheduled to attend the Coaching session will receive a mailing with another copy of their ASK report to refer to during the session, and (1) a welcome letter, (2) a copy of the Coaching Powerpoint slides, (3) the “I have a voice” patient handout to prepare for medical visits, and (4) instructions for using the Zoom conferencing system. (See attachments – Coaching session welcome letter, ASK Coaching Powerpoint Slides, I Have a Voice patient handout, and Zoom Instructions).

At the end of the Coaching session, participants will be introduced to a study website that integrates for easy access publicly available patient information about managing arthritis. See attached ASK Website Outline, including both text and informational web-links as well as the ASK Annotate Report for Patients, which will be available on the site. The website links patients to professional society information (e.g., American Association of Orthopedic Surgeons, American Physical Therapy Association) and patient advocacy information (e.g., Arthritis Foundation).

After the Coaching session, participants will receive two emails and one postcard:

- (1) Sharing the link to the study website, and asking participants if they choose to share the ASK report with their primary care provider. If they choose to share it, participants will reply to the email granting permission and include the name and email address of the provider. If they choose not to share, they will do nothing.

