- (1) Asking participants to complete a brief web-based evaluation of the Coaching session. The assessment will ask questions about what was learned from the coaching session, confidence related to managing treatment, and understanding of the OA Care plan. (Attached – ‘Post-Coaching Evaluation Email’ and ‘Post-Coaching Evaluation Survey’). Up to 3 reminder emails (Attached – ‘Post-Coaching Evaluation Email Reminder’) and a phone call to complete the coaching evaluation may be sent/made.

INVESTIGATOR STUDY PLAN

12.14.2021

In addition to phone calls, we will also use text messages to schedule calls with patients. Participants will not complete any study documents through text so no protected health information will be transferred. Patients have been requesting text communication and already provide their phone number at the initial enrollment. We will use existing scripts, emails and letters that have already been approved by the IRB in our text message communication.

(SEE REVISED DETAILS BELOW)

We will also provide participating sites/surgeon offices with a poster that includes their site name (see attached ASK poster) to hang in patient waiting rooms and patient brochures (see attached ASK patient brochure) for sites to distribute as they wish, including in waiting rooms or in clinic materials mailed to new patients in anticipation of their appointment.

From time to time surgical office staff members take time off, so at these times we will train additional office staff to enter new-visit patients into the study's web-system. With PCORI's support, we may offer cookies or other edible item for office staff to share following re-training if they continued to meet the enrollment standards. We ensure that the enrollment standards are attainable based on reviewing our detailed records of historical enrollment rates at each site. This case finding step is viewed as "usual care," and the office staff who receive the edible item are distinct from the research staff who invite study participation (consent). In total, up to \$60 (cookies or other edible item) *10 offices = \$600 per year may be allocated to these costs.

Procedures to invite patients to participate in the Aim 3 Patient Qualitative Interviews

Goals:

- Understand patients' perspectives of OA Care plan when choosing surgery or non-surgical care.
- Understand patients' perspectives of A.S.K. Coaching session.

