After the research coordinator completes the verbal consent process, the 1-month Decisional conflict assessment, and the invitation to the ASK Coaching session AND the patient schedules a Coaching session, the coordinator will invite the patient to the Interview (See 'Aim 3 Patient Interview – Additions to Invitation Phone Call'). The coordinator will review the Aim 3 Patient Interview Fact Sheet and answer questions. The modified recruitment script will be used until interviews are completed. Interviews will take place within 2-4 weeks of coaching session and within 6-8 weeks of office visit with surgeon. Patients who schedule an interview will receive 2 additional emails: 1 with a copy of their personalized report for reference during the interview ('Aim 3 Patient Interview – Report Email') and 1 as a reminder of their session ('Aim 3 Patient Interview – Reminder Email').

For all patients:

Participation in interviews is voluntary. The interview is 1:1, will take up to 1 hour (estimated 30-60 minutes), and uses a virtual web-platform (Zoom). Participants can also opt to join by phone alone. Sessions will be scheduled at various times of day to meet patients' needs. Trained interviewers will use a semi-structured discussion guide (see attached 'Aim 3 Patient Interview Guide'). With participants' verbal consent, interviews will be audio-recorded. Participants will receive a \$20 gift card after completing the interview in appreciation for their time.

Twenty-five interviews were completed as planned in 2021. In 2022, we plan to interview an additional twenty-five patients at two time points, pre and post coaching. The consent plan and reminder emails will match the initial twenty-five interviews. An updated interview guide is attached.

Qualitative interview of the surgeons to get their feedback on the report.

Goals: Conduct interviews of all participating surgeons, as possible, to:

1. Assess surgeon use of each component of the ASK report- how was it used? in which patients?

INVESTIGATOR STUDY PLAN

12.14.2021

p1- descriptive data: (a) symptom severity/PROs, (b) clinical risk profile
p2- predictive data for surgical treatment: (a) predicted scores, (b) predicted symptoms
p3- comparative grid of non-operative options

2. When ASK report is not used; why not? (office flow or time? patient factors? report content?) If due to report- what modifications (if any) would improve the report?
3. What office systems facilitated use? limited use?

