10. STUDY ENDPOINTS*

Primary Outcomes Measures:

1. To assess the effect of OA Careplan on (a) decision quality using a validated Decisional Conflict Scale and (b) pre-to-post decision pain relief and functional gain, using the HOOS (for hip patients) or KOOS (for knee patients).
2. To evaluate the effect of the OA Careplan+Support on (a) decision quality using Decisional Conflict Scale and (b) pre-to-post decision pain relief and functional gain, using the HOOS or KOOS.

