11. PROCEDURES INVOLVED*

See #8 above

Surgeon offices will be randomized to Usual Care or Intervention sites. During Aim 2, after completing the surveys in the clinic, usual care patients and surgeons will have the ability to

INVESTIGATOR STUDY PLAN

12.14.2021

see PRO scores, but will NOT receive feedback (no OA Care Plan) as PROs are the current standard of care in orthopedic clinics. For intervention sites, the patient and surgeon will receive the OA Care Plan (now called A.S.K. report). In Aim 3 (see details above), all patients (both study arms) will receive the A.S.K. report. In addition, patients at intervention sites will be invited to attend the ASK Coaching session to review the content of the report, discuss how to use the report in communication with the medical team, and to learn more about arthritis self-care.

Data collected include the following: New Patient Baseline [Knee/Hip] surveys; 1-month Decisional Conflict Scale;), 6-month and 12-month [Knee/Hip] surveys attached). These data collection sheets will be submitted to the IRB once they are developed.

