satisfaction with the OA care decision, as compared to usual care. Further, we hypothesize that improved decision quality will mediate quality of OA care as measured by lower pain and higher function at 6 and 12 months (KOOS/HOOS) after decision for both TJR and non-operative care. In Aim 3, we hypothesize that the OA Careplan+Support (vs. OA Careplan alone) will incrementally enhance decision quality and quality of OA care (for those who choose to use the Support) with the same measures used in Aim 2.

The general analytic approaches for Aims 2 and 3 are similar and summarized here. The underlying models extend our previous award-winning TKR outcome prediction model where discrete outcome sub-groups were identified. We will adhere to the intent-to-treat principle to analyze the trial data; the intervention status of the surgeon/site and their patients will be analyzed according to their status at the time of intervention. First, descriptive statistics for all relevant outcomes will be tabulated by treatment arm. Select patient factors (e.g., race, sex, function; comorbid factors) that may contribute to heterogeneity of treatment effects will be compared using univariate methods such as t-test for normally distributed variables, Wilcoxon rank sum test for skewed continuous variables, or Chi² test for categorical variables. We will examine distributions of outcomes, identify proper distribution assumptions, and determine whether or what types of transformations are indicated.

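### As written, Aim 3's primary Decisional Conflict Scale is completed before the coaching invitation, so it cannot show an effect of delivered Support

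*Combined protocol and SAP*

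**What the plan says.** Section 10 lists among the primary outcomes: "To evaluate the effect of the OA Careplan+Support on (a) decision quality using Decisional Conflict Scale". The section 13 overview expects Support to improve "decision quality and quality of OA care (for those who choose to use the Support) with the same measures used in Aim 2".

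Section 8 describes how coaching is offered: "After the research coordinator completes the verbal consent process and the 1-month Decisional conflict assessment, s/he will then invite the patient to participate". The procedure for inviting Enhanced-arm patients to interview repeats the order; that invitation follows consent, then "the 1-month Decisional conflict assessment, and the invitation to the ASK Coaching session AND the patient schedules a Coaching session".

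The other Support components come later still. On the website: "At the end of the Coaching session, participants will be introduced to a study website". Permission to share the report with the primary care provider is sought by email after the session. The only Enhanced-arm material described before the DCS is a fact sheet and a flyer in the recruitment packet.

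Section 11 gives the measurement schedule: "Data collected include the following: New Patient Baseline [Knee/Hip] surveys; 1-month Decisional Conflict Scale;), 6-month and 12-month [Knee/Hip] surveys attached". Section 8 agrees and pairs the Shared Decision Making Process Survey with the DCS at 1 month. The web survey after coaching goes to coaching participants only and is summarised as covering "questions about what was learned from the coaching session, confidence related to managing treatment, and understanding of the OA Care plan"; the DCS is not among these.

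For Aim 3, section 13 plans an arm comparison, inverse-propensity weighting on use of Support, a pre-post comparison with Aim 2 for the same surgeons, a usage dose-response analysis, and a mediation test.

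**The concern.** An outcome can reflect only what came before it. If the DCS is complete before a patient is invited to coaching, then coaching, website and primary care sharing cannot have moved it. One of Aim 3's two primary outcome domains would be recorded before the intervention it is meant to evaluate.

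Both possible results would mislead. A null DCS contrast could be read as Support failing to improve decisions. A difference could be credited to coaching that nobody had yet received. Section 13 offers a rival explanation for such a difference: the Enhanced arm includes the 20 surgeons who already used the Careplan in Aim 2, while the former usual-care surgeons start using it in Aim 3.

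In analyses by use of Support the association could also run backwards, because decisional conflict at 1 month may influence who then attends.

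**Working it through.** **1. The plan's own figure.** Inputs from section 13: 40 surgeons in two equal arms, 100 patients per surgeon, intraclass correlation 0.02, 5% significance (two-sided assumed), power at least 80%.

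- Design effect = 1 + (100 − 1) × 0.02 = 2.98.
- Effective patients per arm = 2,000 / 2.98 = 671.
- Detectable difference = (1.96 + 0.84) × √(2/671) = 0.153 SD, or 0.157 SD with t quantiles on 38 degrees of freedom. This rounds to the stated 0.16 SD.
- Power at 0.16 SD is 83.4%.

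With the revised section 4 size of 3,000 patients and 40 surgeons (75 each), the design effect is 1 + 74 × 0.02 = 2.48, the effective number per arm is 1,500 / 2.48 = 605, and the detectable difference is 0.161 SD. The arithmetic is sound. The question is what it applies to.

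**2. Order of events for an Enhanced-arm patient, from section 8.**

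| Step | Event |
|---|---|
| 1 | Recruitment packet with coaching fact sheet and flyer |
| 2 | Verbal consent |
| 3 | 1-month DCS |
| 4 | Coaching invitation, then scheduling |
| 5 | Coaching session; website introduced at its end |
| 6 | Emails: primary care sharing, coaching evaluation |
| 7 | 6- and 12-month HOOS/KOOS |

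Steps 4 to 6 are the Support and all follow step 3. Only step 7 can register them. Confidence items appear on the Enhanced arm's 1-month form and again in the post-coaching survey, which fits the 1-month form being the pre-coaching measure.

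**3. What delivered Support can contribute to the DCS contrast.** Let f be the share of Enhanced-arm patients whose DCS follows coaching, and d the effect in those patients. Contribution = f × d. This assumes that the fact sheet and flyer have no effect. As written, f = 0, so the contribution is 0 SD. With no other arm difference, the test rejects at its 5% level, whatever the sample size.

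The non-zero shares below are assumptions, because the documents give no dates. Power is for 3,000 patients and 40 surgeons; counts assume 1,500 Enhanced-arm patients.

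| f | Patients | Contrast if d = 0.16 SD | Power | d needed for 0.16 SD (0.16/f) |
|---|---|---|---|---|
| 0 (as written) | 0 | 0 | 5.0% | none suffices |
| 10% | 150 | 0.016 | 5.9% | 1.60 |
| 25% | 375 | 0.040 | 10.7% | 0.64 |
| 50% | 750 | 0.080 | 28.5% | 0.32 |
| 100% | 1,500 | 0.160 | 79.5% | 0.16 |

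**4. Do the interview windows change the order?** "Interviews will take place within 2-4 weeks of coaching session and within 6-8 weeks of office visit with surgeon". Read as ranges, coaching falls between week 6 − 4 = 2 and week 8 − 2 = 6 after the visit, on either side of a 1-month DCS. The windows alone do not settle the order; the two statements of sequence do.

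**5. Analyses affected (section 13).**

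- Inverse-propensity weighting: decision quality is named as an outcome. Affected.
- Pre-post comparison: decision quality is named. Affected.
- Usage dose-response: the outcomes are left general. Affected only if decision quality is among them.
- Careplan+Support mediation: the test names no mediator, though the overview hypothesis points to decision quality. Affected if that is the mediator.
- The 1-month Shared Decision Making Process Survey has the same timing as the DCS.

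**The case against.** The strongest reply is that the documents do not prove that no DCS follows coaching. The post-coaching, 6-month and 12-month surveys are attachments that were not available. Section 10 gives the DCS no time point. The section 4 wording of Aim 2 mentions 6 and 12 months in a sentence that also covers decision quality. Surveys may be mailed or emailed, website access is mentioned once without a time, and the interview windows would permit coaching before week 4.

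Much of this stands as a limit on certainty, and it is why the attachments and dates come first in the remedy. It does not overturn the point. In section 4 the 6- and 12-month phrase most naturally belongs to pain and function. No rule requires a DCS after coaching, so late forms would be incidental and the contrast diluted.

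A second reply is that intention-to-treat evaluates the offer of Support. But the coordinator's invitation also follows the DCS. The contrast captures at most the packet materials and differences between surgeons.

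A reader might infer more than the text supports:

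- That Aim 3 cannot evaluate Support at all. The 6- and 12-month HOOS/KOOS outcomes come after coaching and remain usable.
- That all 3,000 patients lack a post-Support DCS. Controls are not offered Support, so the relevant group is about 1,500.
- That the dose-response analysis is specified for decision quality. Section 13 does not name it there.
- That every DCS in fact preceded coaching. The plan states the order; only recorded dates can show what happened.

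**Conclusion.** The point holds for the plan as written. Two places in section 8 put the completed DCS before the coaching invitation, the other Support components come later, and the text describes no further DCS. Delivered Support therefore contributes 0 SD to this primary outcome in the roughly 1,500 Enhanced-arm patients, and the stated power does not apply to delivered Support on the DCS. Two analyses that name decision quality reverse exposure and outcome; the dose-response and mediation analyses do so under the conditions given above.

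This rests on an equal split of 3,000, on the described sequence being followed, and on the attachments containing no later DCS collected comparably in both arms. It is an error of order rather than missing detail, and it should be corrected before outcome analysis.

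**What to change.** Document the following before outcome analysis:

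1. Check the survey attachments for any later DCS. Compare recorded DCS and coaching dates, and report how many Enhanced-arm forms precede coaching.
2. Unless these show a post-coaching DCS collected comparably in both arms, keep the intention-to-treat DCS contrast but label it as measured before coaching (or mostly so, giving the share), and not as evidence for or against delivered Support.
3. On the same condition, remove the DCS and the 1-month Shared Decision Making survey as outcomes from the Support-use, dose-response and pre-post analyses, and do not use the DCS as a mediator of Support.
4. On the same condition, state that Aim 3 conclusions about Support rest on 6- and 12-month HOOS/KOOS pain and function.

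The DCS should not be entered in the use-propensity model only for patients whose form precedes coaching: the covariate would then be missing by exposure status.

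A repeat DCS in both arms is optional. The plan is dated 12.14.2021 and enrolment ends about March 1, 2022, so it would cover only late enrollees, at one short extra contact each.

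The cost is a date check and changes to endpoint and analysis wording. Funder and IRB agreement may be needed, as earlier design changes went to the funder. The downside is that Aim 3 loses decision quality as evidence on Support.

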9. STUDY TIMELINES*

Aim 1 Interviews (in place of Focus Groups)

Individual participants will complete an interview lasting approximately 60 minutes.

We anticipate that we can recruit within 6 months.

We anticipate an additional 6 months to complete data analyses.

Aims 2 and 3

Participants will participate in the study for approximately 1 year, from the time of treatment decision to completion of the 12 month FU survey.

We anticipate that it will take approximately 1.5 years to recruit 3000 for Aim 2 and 1.5 years to recruit for Aim 3.

We anticipate that primary analyses will be completed in 5 years (2022).

10. STUDY ENDPOINTS*

Primary Outcomes Measures:

1. To assess the effect of OA Careplan on (a) decision quality using a validated Decisional Conflict Scale and (b) pre-to-post decision pain relief and functional gain, using the HOOS (for hip patients) or KOOS (for knee patients).
2. To evaluate the effect of the OA Careplan+Support on (a) decision quality using Decisional Conflict Scale and (b) pre-to-post decision pain relief and functional gain, using the HOOS or KOOS.

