12. DATA AND SPECIMEN BANKING*

No specimens will be banked for future use. See #13, Data Management, for data retention and access.

13. Data Analysis and Management*

Responsibility for 6 month and 12 month outcome data collection was transferred from UMMS to Northwestern during 2021. At the completion of study enrollment (on or about March 1, 2022), the UMMS data enrollment and collection services will be completed. At that date, the UMMS data center will have already, or will then, transfer all enrollment, patient-reported, and study data to Northwestern for the analytic team to manage and analyze. The UMMS data center will confirm that they expunged all ASK study data from the web-based data capture systems (DatStat, RedCap) and UMMS data storage files within UMMS.

Aim 1

We will transcribe recorded interviews and code using content analysis techniques to identify themes. We expect to achieve data saturation at or before completing 30 interviews with patients and 30 with caregivers.

AIM 2 and 3. Sample size and effect size estimates:

The trial is designed with $\geq 80\%$ statistical power at 5% significance level to detect intervention effects that are meaningful to both patients and surgeons, and health systems. In total, 40 (Aim 2) or 54 (Aim 3) surgeons will be randomized equally to treatment and control arms with an average of 100 patients/surgeon. Based on data from FORCE-TJR, the intraclass correlation within surgeon is approximately 0.02. Using two independent group t-tests adjusting for within surgeon clustering, the trial can detect an intervention effect of (a) improved decision quality of >0.16 SD ; (b) improved quality of OA care defined in two ways: 6 month post-decision pain relief (KOOS/HOOS) of ≥ 3.3 points for TKR patients (34.1 vs. 37.4; SD=20.8) and ≥ 3.3 for THR patients (45.7 vs. 49.0; SD=20.9) or greater proportion of patients with meaningful pain relief (17 points in HOOS/KOOS pain score) of $\geq 6.1\%$ more TKR patients (77.9% vs. 84.0%) and $\geq 4.2\%$ more THR patients (90% vs. 94.2%).

Aims 2 and 3: Overview of analytic approach. We hypothesize (Aim 2) that patient/clinician use of the OA Careplan will improve decision quality as well as

INVESTIGATOR STUDY PLAN

12.14.2021

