will be entered into the same model in order to assess their contributions to the outcome under analysis, after adjusting for each other, as well as the patient-level covariates. Model assumptions will be carefully examined. In these model-building processes, effect modifications will be examined by including interaction terms between relevant covariates, and to ensure the heterogeneity of the intervention effects among patient subgroups are adequately considered. The analyses will be conducted with all patients; and then for TKR and THR patients separately. While the primary goal is to understand patient-level covariates with outcomes, it is critical to assess surgeon/site factors that may influence outcome for all, or sub-groups of patients. For example, obese, diabetic patients with cardiac disease may have more positive decision quality and pain relief with a more experienced high-volume surgeon.

Aim 2: To assess the effect of OA Careplan on (a) decision quality and (b) pre-to- post decision pain relief and functional gain, we will do the following. We expect 20 surgeons and 2000 patients will receive the OA Careplan intervention, and another 20 surgeons and 2000 patients will receive usual care. The analyses will be conducted with all patients; and then for TKR and THR patients separately. First, we will tabulate the decision quality and care outcomes by arm and for select patient subgroups (e.g., sex, age, race/ethnicity). Second, we will use GLLAMM to estimate adjusted Careplan intervention effects by including in the models a Careplan indicator (Careplan intervention=1 vs. usual care=0) and a set of site/surgeon and patient variables for adjustment. A statistically significant coefficient of the Careplan indicator signals possible intervention effect. In this analysis, interaction terms between the Careplan indicator and surgeon or patient factors will be examined, statistically significant interaction terms may suggest the existence of heterogeneity in intervention effects. If present, intervention effects will be analyzed and presented by subgroups.

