Second, we will use GLLAMM to analyze the differences in joint pain and function at 6 and 12 months after the care decision between OA Careplan and comparison arms. We will pool data from both arms in the two phases. We will include an indicator variable to represent intervention status (usual care, OA Careplan, or OA Careplan+Support). We will assess whether 6 and 12 month pain differ between intervention arms. Next, we will repeat this process for the patients with meaningful (>17 point) change in HOOS/KOOS pain score. We expect pain relief will be significantly improved in the OA Careplan arm, with greater improvement to occur in the OA Careplan+Support, compared to the usual care group. Finally, we will formally test the mediation effects of Careplan and Careplan+Support on pain relief and functions at 6 and 12 months, using the two level structural equation models with mediation effects by Krull and MacKinnon (2001) and Preacher, Zyphur and Zhang (2010).

Only those listed in our IRB application will have access to identified data.

At this time, there is no plan to destroy the Patient Reported Outcome (PROs) data because of the value to this data regarding national norms for PROs for patients electing to have surgery and those electing non-surgical management of OA.

PHI including individual contact information for follow-up date collection will be destroyed after all surveys have been completed by individual patients 3 years after the completion of the study.

Published data derived from this study will consist of statistical analyses collapsed (averaged) across participants. Under no circumstances will data from individual participants be identifiable in reports or published manuscripts.

INVESTIGATOR STUDY PLAN

12.14.2021

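### The quality-of-care hypothesis in each aim has several routes to significance and no named deciding test, so the 5% level does not hold for that claim

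*Combined protocol and SAP*

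**What the plan says.** Section 10 names, as primary for each aim, "a) decision quality using a validated Decisional Conflict Scale and (b) pre-to-post decision pain relief and functional gain", with pain and function measured by HOOS or KOOS. It gives no order, time point or population.

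Section 13 (sample size paragraph) claims at least 80% "statistical power at 5% significance level to detect intervention effects". It then describes "improved quality of OA care defined in two ways": mean 6-month pain relief, *or* the proportion with a 17-point pain improvement. Each is given separately for TKR and THR.

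The rest of Section 13 widens the set of tests:
- The overview takes quality of care to be pain and function at both 6 and 12 months.
- "The analyses will be conducted with all patients; and then for TKR and THR patients separately".
- For Aim 2, "A statistically significant coefficient of the Careplan indicator signals possible intervention effect". The Aim 3 text uses similar wording for Support.
- In the pooled analysis, "We will assess whether 6 and 12 month pain differ between intervention arms", after which the process is repeated for the 17-point responder outcome.

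No section gives a hierarchy, a split of alpha, a multiplicity adjustment or a rule that several outcomes must all succeed. The only other threshold is p<0.10, used to select covariates.

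**The concern.** Decision quality and quality of care are two distinct questions, and whether alpha should be shared between them is debatable. The difficulty here lies inside the second question. One claim, that the Careplan (or Support) improves quality of care, can be supported by any of several results, and the plan does not say which one decides it. If each is judged at 5%, the chance of a false claim exceeds the stated level. The deciding result could also be picked after the estimates are seen. A reader of the final report could not tell whether a significant 12-month function result in THR patients, for example, confirms the hypothesis or is one of many looks.

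**Working it through.** **1. What the 5% refers to.** Inputs from Section 13: 40 surgeons in Aim 2, 100 patients each (2,000 per arm), ICC 0.02, SD 20.8 (TKR) and 20.9 (THR).
- Design effect = 1 + (100 − 1) × 0.02 = 2.98; effective n = 2000/2.98 = 671 per arm.
- Decision quality, 0.16 SD: power = Φ(0.16/√(2/671) − 1.960) = Φ(2.931 − 1.960) = 83.4%.
- Pain, 3.3 points: TKR 82.8%, THR 82.4%. With a t reference on 38 df, the three powers are 81.5%, 80.8% and 80.5%.
- Responders: TKR 77.9% vs 84.0%, power 81.3%; THR 90% vs 94.2%, power 81.5%.

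The plan's figures reproduce, each as a single two-sided 5% test. Nothing has been set aside for multiple tests.

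**2. Tests within hypothesis (b), per aim, leaving out the Decisional Conflict Scale.**
- Pain and function × 2 times, all patients: 4 tests.
- The same in all, TKR and THR patients: 12 tests.
- Adding the responder outcome: 3 outcomes × 2 times × 3 populations = 18 tests.

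**3. Chance of at least one false positive when nothing works.** For 4 independent tests: any direction 1 − 0.95⁴ = 18.5%; false benefit only 1 − 0.975⁴ = 9.6%. The documents give no correlations, so I simulated normal test statistics with a common correlation r across outcomes and times. The TKR share was assumed to be 60%, with the all-patient statistic formed as √0.6 × TKR + √0.4 × THR.

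| Tests | r = 0.5 | r = 0.7 | r = 0.9 |
|---|---|---|---|
| 4, any direction | 16% | 13% | 9% |
| 4, false benefit | 8% | 7% | 5% |
| 12, any direction | 33% | 28% | 20% |
| 12, false benefit | 17% | 14% | 10% |
| 18, any direction | 42% | 34% | 23% |
| 18, false benefit | 22% | 18% | 12% |

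The benchmark is 5% for any direction and 2.5% for false benefit. If the correlation weakens further when both outcome and time differ, the any-direction rates are 21% to 34% (12 tests) and 26% to 43% (18 tests).

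**4. The sample size paragraph alone.** Two definitions × two joints at 6 months is 4 tests: 18.5% if independent, about 14% to 16% with mean pain and responder status correlated 0.9 to 0.7.

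**5. Cost of controlling error across (a) and (b) as well.** The first Holm step uses 2.5%: (2.241 + 0.842)/(1.960 + 0.842) = 1.10, so 0.16 SD becomes 0.176 SD. Power at 0.16 SD falls to Φ(2.931 − 2.241), about 75%.

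**The case against.** The strongest reply is that most of the alternatives are read into silence. Section 10 joins pain relief and functional gain with *and*, and the overview in Section 13 does the same. The only *or* in the text joins two scalings of the same 6-month pain score, which by itself is two tests (1 − 0.95² = 9.75% if independent, less when correlated). If pain and function both had to succeed, error would not be inflated. The planned repeated-measures model has one Careplan indicator, so both times might share a coefficient. All patients come first in the text, which suits a reading of TKR and THR as supportive.

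This stands in part. The conjunctive reading is possible but not stated, and no rule rules out the others. Section 13 also assesses pain at 6 and 12 months without making either time decisive, and it states detectable pain effects by joint, so the joints are not plainly secondary.

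Three stronger readings are not supported:
- A reader might count the Decisional Conflict Scale too and quote 1 − 0.95⁵ = 22.6% as the error of the quality-of-care claim. That scale belongs to hypothesis (a), so the figure describes a different family.
- A reader might infer that the plan declares success on any significant result. It speaks only of a *possible* effect, and it states 5% once, in the sample size paragraph. Testing each result at 5% is an inference.
- A reader might say that the risk of wrongly claiming benefit is several times 5%. Two-sided counts include false harm. For the 4-test family false benefit is about 5% to 10%, to be compared with 2.5%.

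**Conclusion.** The concern holds for hypothesis (b) of each aim: as written, the plan does not say which outcome, time and population decide it, so the 5% level is not secured for that claim. In the narrowest family (4 tests, all patients) the any-direction rate is about 9% to 16% under the assumed correlations and 18.5% under independence. False benefit is about 5% to 10% against 2.5%. Counting the by-joint repeats gives about 20% to 33% (false benefit 10% to 17%), and adding responders about 23% to 42% (false benefit 12% to 22%).

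These ranges rest on assumed correlations of 0.5 to 0.9, a 60% TKR share, testing each result at 5%, and *all patients* meaning knee and hip combined. The size is uncertain, but under these assumptions every family exceeds its benchmark. A stated rule that pain and function must both succeed would remove the inflation between those two outcomes; the documents contain no such rule. This should be corrected before the arms are compared.

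**What to change.** For each aim, in Sections 10 and 13:
- Keep the Decisional Conflict Scale as the deciding test for hypothesis (a). It need not act as a gate for pain.
- For hypothesis (b), name mean 6-month HOOS/KOOS pain change in all patients as the deciding test at 5%. This is the outcome and time that Section 13 already powers.
- Then test functional gain and the 12-month results in a stated fixed sequence, each at 5% and only if the preceding test succeeds. They keep a confirmatory role.
- Label the responder proportion and the separate TKR and THR analyses supportive.
- State the detectable effect for the pooled population. Section 13 gives it only by joint, and its figures reproduce only if each joint has all 2,000 patients per arm. At the 3,000 patients of Section 4 (75 per surgeon), the design effect is 1 + 74 × 0.02 = 2.48 and effective n is 1500/2.48 = 605 per arm. Power at 3.3 points is then about 79% with SD 20.8.

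Cost: no change to data collection, but more than a wording change to the analysis section, because the endpoint section must be edited. Function and 12-month results become confirmatory only if 6-month pain succeeds. The 6-month pain test itself loses no power. If the sponsor also wants 5% control across (a) and (b), Holm over the two deciding tests raises the worst-case detectable effect by about 10% (0.16 to 0.176 SD), or lowers power at 0.16 SD from about 83% to 75%.
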